### **RAS and BRAF mutation detection using circulating free DNA (cfDNA)**

Currently the detection of RAS and BRAF mutations is carried out in tumor tissue by NGS. This requires bone marrow aspiration for derivation of tumor tissue and CD138 purification of myeloma tumor cells for DNA extraction. Recent studies have validated the detection of KRAS and BRAF mutations from circulating free tumor DNA (cfDNA). cfDNA was detected in 100% of patients with metastatic colorectal cancer and showed 100% specificity and sensitivity for BRAFV600E mutation and 98% specificity and 92% sensitivity for KRAS mutations (*Thierry AR et al. 2014*). Thus this represents a minimally invasive and cost-effective method for identification of patients that are most likely to benefit from targeted therapy. We postulate that patients with MM will similarly have detectable cfDNA and that mutations of RAS and RAF can be efficiently and effectively detected from cfDNA.

## **3 PATIENT SELECTION**

### **3.1 Eligibility Criteria**

3.1.1 Patients must have histologically or cytologically confirmed Multiple Myeloma NOS (10028566).

- 3.1.2 Patients must have measurable disease as defined as at least one of the following (these baseline laboratory studies for determining eligibility must be obtained within 28 days prior to start of protocol therapy):
- Serum M-protein  $\geq 0.5$  g/dl ( $\geq 5$  g/l)
  - Urine M-protein  $\geq 200$  mg/24 h
  - Serum free light chains (FLC) assay: Involved FLC level  $\geq 10$  mg/dl ( $\geq 100$  mg/l) and an abnormal serum free light chain ratio ( $< 0.26$  or  $> 1.65$ )
  - Biopsy proven plasmacytoma (should be measured within 28 days of first study drug administration). Prior biopsy is acceptable.
  - If the serum protein electrophoresis is unreliable for routine M-protein measurement, quantitative immunoglobulin levels on nephelometry or turbidometry will be followed.
- 3.1.3 A diagnosis of MM and documentation of relapsed or relapse/refractory status following at least 2 prior lines of therapy.
- 3.1.4 Documented lab results confirming tumor mutational status (as outlined in [Appendix F](#), Table 3) must be obtained at screening. Patients in whom mutational status cannot be determined will be deemed ineligible.
- 3.1.5 Because no dosing or adverse event data are currently available on the use of trametinib with and without GSK2141795 in patients  $< 18$  years of age, children are excluded from this study.
- 3.1.6 ECOG performance status  $\leq 2$  (Karnofsky  $\geq 60\%$ , see [Appendix A](#)).
- 3.1.7 Life expectancy of greater than 6 months.
- 3.1.8 Able to swallow and retain orally-administered medication and does not have any clinically significant gastrointestinal abnormalities that may alter absorption such as malabsorption syndrome or major resection of the stomach or bowels.
- 3.1.9 All prior treatment-related toxicities must be CTCAE v4 grade  $\leq 1$  (**except alopecia**) at the time of registration. Subjects with toxicities attributed to prior anti-cancer therapy which are not expected to resolve and result in long lasting sequelae are permitted to enroll.
- 3.1.10 Patients must have normal organ and marrow function as defined below:
- Absolute neutrophil count (ANC)  $\geq 1.0 \times 10^9/L$
  - Hemoglobin  $\geq 8$  g/dL
  - Platelets  $\geq 50 \times 10^9/L$
  - Albumin  $\geq 2.5$  g/dL
  - Total bilirubin  $\leq 1.5 \times$  institutional ULN (isolated bilirubin  $> 1.5 \times$  ULN is acceptable if bilirubin is fractionated and direct bilirubin  $< 35\%$ )
  - Aspartate aminotransferase (AST) and alanine aminotransferase (ALT)  $\leq 2.5 \times$  institutional ULN

- Serum creatinine  $\leq 1.5$  mg/dL *OR* calculated creatinine clearance (Cockcroft-Gault formula)  $\geq 30$  mL/min *OR* 24-hour urine creatinine clearance  $\geq 30$  mL/min
- Prothrombin time (PT)/International normalized ratio (INR) and partial thromboplastin time (PTT)  $\leq 1.5$ x institutional ULN
- Fasting serum glucose  $< 126$  mg/dl (7 mmol/l)
- Left ventricular ejection fraction (LVEF)  $\geq$  institutional lower limit of normal (LLN) by ECHO or MUGA

3.1.11 Subjects that have been previously diagnosed with Type 2 diabetes or steroid-induced diabetes must also meet the additional following criteria:

- Diagnosed with diabetes  $\geq 6$  months prior to enrolment
- HbA1C  $\leq 8\%$  at screening visit

3.1.12 The effects of trametinib *or* GSK2141795 on the developing human fetus are unknown. For this reason and because MEK inhibitors as well as other therapeutic agents used are known to be teratogenic, women of child-bearing potential and men must agree to use adequate contraception (hormonal or barrier method of birth control; abstinence) prior to study entry and for the duration of study participation. Women of child-bearing potential must have a negative serum pregnancy test within 7 days prior to the start of protocol therapy. Should a woman become pregnant or suspect she is pregnant while she or her partner is participating in this study, she should inform her treating physician immediately. Men treated or enrolled on this protocol must also agree to use adequate contraception prior to the study, for the duration of study participation, and 4 months after completion of trametinib administration.

3.1.13 Ability to understand and the willingness to sign a written informed consent document.

## 3.2 Exclusion Criteria

3.2.1 History of another malignancy.

Exception: Patients who have been disease-free for 3 years, or patients with a history of completely resected non-melanoma skin cancer and/or patients with indolent second malignancies, are eligible. Consult the CTEP Medical Monitor if unsure whether second malignancies meet the requirements specified above.

3.2.2 History of interstitial lung disease or pneumonitis.

3.2.3 Diabetes mellitus currently requiring insulin. Subjects with a history of steroid-induced hyperglycemia may be enrolled provided that HbA1C at screening visit is  $\leq 8\%$ .

- 3.2.4 Any major surgery, extensive radiotherapy, chemotherapy with delayed toxicity, biologic therapy, or immunotherapy within 28 days prior to randomization and/or daily or weekly chemotherapy or other approved anti-myeloma therapy without the potential for delayed toxicity within 14 days prior to registration.
- 3.2.5 Use of other investigational drugs within 28 days preceding the first dose of trametinib and during the study.
- 3.2.6 Symptomatic or untreated leptomeningeal or brain metastases or spinal cord compression.
- 3.2.7 Have a known immediate or delayed hypersensitivity reaction or idiosyncrasy to drugs chemically related to trametinib or excipients or to dimethyl sulfoxide (DMSO) or GSK214795.
- 3.2.8 Current use of a prohibited medication. The following medications or non-drug therapies are prohibited:
- Other anti-cancer therapy while on study treatment. (note: megestrol [Megace] if used as an appetite stimulant is allowed).
  - Concurrent treatment with bisphosphonates is permitted; however, treatment must be initiated prior to the first dose of study therapy. Prophylactic use of bisphosphonates in patients without bone disease is not permitted, except for the treatment of osteoporosis.
  - Because the composition, PK, and metabolism of many herbal supplements are unknown, the concurrent use of all herbal supplements is prohibited during the study (including, but not limited to, St. John's wort, kava, ephedra [ma huang], ginkgo biloba, dehydroepiandrosterone [DHEA], yohimbe, saw palmetto, or ginseng).
- 3.2.9 *In vitro* data indicate that GSK2141795 is a CYP3A4 substrate. Drugs that potently inhibit CYP3A4 could lead to increased GSK2141795 exposure in subjects, and should either be prohibited or used with caution. Drugs which are strong inducers of CYP3A4 and may result in lower exposures of GSK2141795 should also be prohibited. GSK2141795 also appears to be a moderate *in vitro* inhibitor of CYP2C8 (50% inhibitory concentration [IC50] 3 mcM) and CYP3A4 (IC50 11 mcM). Drugs that are substrates of CYP3A4 or CYP2C8 with a narrow therapeutic index may be prohibited. Drugs that are sensitive substrates of CYP3A4 or CYP2C8 should be used with caution. (Refer to 5.2.3)
- 3.2.10 History or current evidence/risk of retinal vein occlusion (RVO) or Retinal Pigment Epithelial Detachment (RPED):
- History of RVO or RPED, or predisposing factors to RVO or RPED (*e.g.*, uncontrolled glaucoma or ocular hypertension, uncontrolled systemic disease such as hypertension, diabetes mellitus, or history of hyperviscosity or hypercoagulability syndromes).
  - Visible retinal pathology as assessed by ophthalmic exam that is considered a risk factor for RVO or RPED such as evidence of new optic disc cupping, evidence of new visual field defects, and intraocular pressure >21 mm Hg.

3.2.11 History or evidence of cardiovascular risk including any of the following:

- LVEF < LLN.
- A QT interval corrected for heart rate using the Bazett's formula  $QTcB \geq 480$  msec ( $\geq 500$  msec for subjects with bundle branch block)
- History or evidence of current clinically significant uncontrolled arrhythmias (exception: patients with controlled atrial fibrillation for >30 days prior to randomization are eligible).
- Other clinically significant ECG abnormalities including 2nd degree (Type II) or 3rd degree atrioventricular (AV) block.
- Subject with intra-cardiac defibrillators or pacemakers.
- History of acute coronary syndromes (including myocardial infarction and unstable angina), coronary angioplasty, or stenting within 6 months prior to randomization.
- History or evidence of current  $\geq$  Class II congestive heart failure as defined by the New York Heart Association (NYHA) functional classification system
- Treatment-refractory hypertension defined as a blood pressure of systolic >140 mmHg and/or diastolic >90 mmHg which cannot be controlled by anti-hypertensive therapy.
- Known cardiac metastases.

3.2.12 Known Human Immunodeficiency Virus (HIV), Hepatitis B Virus (HBV), or Hepatitis C Virus (HCV) infection (with the exception of chronic or cleared HBV and HCV infection, which will be allowed).

3.2.13 Uncontrolled intercurrent illness including, but not limited to, ongoing or active infection, symptomatic congestive heart failure, unstable angina pectoris, cardiac arrhythmia, or psychiatric illness/social situations that would limit compliance with study requirements.

3.2.14 Animal reproductive studies have not been conducted with trametinib. Therefore, the study drug must not be administered to pregnant women or nursing mothers. Women of childbearing potential should be advised to avoid pregnancy and use effective methods of contraception. Men with a female partner of childbearing potential must have either had a prior vasectomy or agree to use effective contraception. If a female patient or a female partner of a patient becomes pregnant while the patient receives trametinib, the potential hazard to the fetus should be explained to the patient and partner (as applicable). These potential risks may also apply to GSK2141795.

### 3.3 Inclusion of Women and Minorities

Both men and women of all races and ethnic groups are eligible for this trial. This study is designed to include minorities as appropriate. However, the trial is not designed to measure differences in intervention effects. The population of Southern Ontario is ethnically diverse and the proportion of different ethnic groups in the community is provided in the table below. Universal access to health care will ensure that there is no discrimination on the basis of race or gender (Guide to Canadian Human Rights Act: [www.chrc-ccdp.ca/public/guidechra.pdf](http://www.chrc-ccdp.ca/public/guidechra.pdf)). Individual hospital registries and databases do not routinely collect racial data, under the direction of the Canadian Human Rights Code.

The population demographics and distribution of minorities in Canada is included in the following table:

**Table: Visible minority population by Consortium Provinces (2001 Census)**

	British Columbia	Alberta	Ontario	Nova Scotia	Total
Total population of province	3,868,870	2,941,150	11,285,550	897,570	18,993,140
Visible Minorities	Population %				
Black	25,465 1%	31,390 1%	411,095 4%	19,670 2%	487,620 3%
Asian	768,435 20%	268,660 9%	1,513,825 13%	12,630 1%	2,563,550 13%
Latin American (Hispanic)	23,880 1%	18,745 1%	106,835 1%	520 0%	149,980 1%
Visible minority, not included elsewhere	4,195 0%	4,220 0%	78,915 1%	1,170 0%	88,500 0%
Multiple visible minority	14,465 0%	6,910 0%	42,375 0%	535 0%	64,285 0%
Total Visible minority population	836,440 22%	329,925 11%	2,153,045 19%	34,525 4%	3,353,936 18%

Source: Statistics Canada, Census of Population.

Data from our consortium has been compiled regarding the representation of minorities on previous clinical trials, and the distribution is as follows:

Population Percentage of Minority and Gender of entering PMHC Trials	2010	2011	2012
Visible Minorities			
Black	0.9	2.3	1.2
Asian	10.1	10.9	11.6
Hispanic	10.1	2.3	3.5
Total	21.1	15.5	16.3
Women	59.6	56.6	44.2

## 4 REGISTRATION PROCEDURES

### 4.1 General Guidelines

The Study Coordinator at the Princess Margaret Consortium Central Office will enter eligible patients on study centrally. All sites should call the Study Coordinator (listed on cover page) to verify biomarker cohort availabilities. The required forms (Eligibility Checklist) will be provided upon site activation.

Following registration, patients should begin protocol treatment within 3 days. Issues that would cause treatment delays should be discussed with the Principal Investigator (cc the central office study coordinator). If a patient does not receive protocol therapy following registration, the patient's registration on the study may be cancelled. The Study Coordinator should be notified

of cancellations as soon as possible.

Except in very unusual circumstances, each participating institution will order DCTD-supplied agents directly from CTEP. A participating site may order agents only after the initial IRB approval for the site has been forwarded by the Coordinating Center to the CTEP PIO ([contact]) except for Group studies.

## **4.2 Registration Process**

Prior to registering a patient, each institution must have submitted all necessary regulatory documentation to the PMH Phase II Consortium Central Office. The eligibility checklist will only be sent once this has been received.

No patient can receive protocol treatment until registration with the Central Office has taken place. All eligibility criteria must be met at the time of registration. There will be no exceptions. Any questions should be addressed with the Central Office prior to registration.

To register a patient, the following documents are to be completed by the research nurse or data manager and sent / faxed to the Central Office Study Coordinator:

- Signed patient consent form
- Eligibility Checklist CRF signed by the investigator

To complete the registration process, central office will review the checklist and once eligibility has been confirmed:

- Assign a patient study number
- Assign the patient a dose
- Register the patient on the study
- Fax or e-mail the confirmation worksheet with the patient study number and dose to the participating site

To ensure immediate attention is given to the faxed checklist, each site is advised to also call the study coordinator listed on the front sheet. Patient registration will be accepted between the hours of 9am to 5pm Monday to Friday, excluding Canadian statutory holidays when the central office will be closed.

## **5 TREATMENT PLAN**

### **5.1 Agent Administration**

Treatment will be administered on an *outpatient* basis. Reported adverse events and potential risks are described in Section 7. Appropriate dose modifications are described in Section 6.1. No investigational or commercial agents or therapies other than those described below may be administered with the intent to treat the patient's malignancy.

Patients will receive trametinib 2 mg taken orally once a day continuously of a 28 day cycle. Patients who develop progressive disease on trametinib monotherapy or achieve less than a PR

after 4 cycles of treatment will have the option to continue on trametinib with the addition of GSK2141795. Progressive disease is defined by the IMWG, however in consultation with the Principle Investigator, GSK2141795 maybe added for progression not yet meeting the IMWG criteria if the treating physician feels that it is in the best interest of the patient. The dosing of trametinib and GSK2141795 will be according to the recommended 1.5 mg trametinib and 50 mg GSK2141795 daily dosing schedule. The patient will be requested to maintain a medication diary of each dose of medication. The medication diary will be returned to clinic staff at the end of each course:

Regimen Description					
Agent	Premedications; Precautions	Dose	Route	Schedule	Cycle Length
Trametinib	Empty stomach; 1 hr before or 2hr after a meal	2mg alone OR 1.5mg in combination with GSK2141795	oral	daily	28 days
GSK2141795	Empty stomach 1 hour after a small snack and 2 hours before a meal	50mg	oral	daily	
**Doses as appropriate for assigned dose level; refer to section 6.1. Please refer to Appendix E for example drug administration regimen of combination treatment					

For patients in whom the trametinib dose during monotherapy has been reduced to 1.5 mg the dose of trametinib will not be further reduced upon the addition of GSK2141795. For patients on trametinib monotherapy who have been dose reduced to 1.0 mg, their dose will remain at 1.0 mg upon the addition of GSK2141795. No dose re-escalation is permitted in the study (except for in the events defined in section 6).

### 5.1.1 Trametinib

The effect of food on trametinib absorption is unknown. The current recommendation is to administer trametinib on an empty stomach, either 1 hr before or 2 hr after a meal; the recommendation to administer trametinib fasting may change based on emerging data.

### 5.1.2 Other Agent(s) GSK2141795

Capsules must be taken fasting 1 hour following a meal and 2 hours before the next meal. Based on nonclinical data and increasing clinical experience, it is possible that GSK2141795 may be a direct gastrointestinal mucosal irritant such that subjects with GI dysmotility or GERD may be predisposed to symptoms of dyspepsia. Therefore, in an effort to decrease this discomfort, we have the following recommendations. The following is recommended:

- Eat a small snack followed by 60 minutes of fasting prior to taking GSK2141795. Water is allowed during this fasting period.

- If possible, take each GSK2141795 capsule approximately 5 minutes apart with divided amounts of fluid (4-8 oz with each capsule for a total of at least 12 oz).
- Remain upright for 30 minutes after taking the last capsule of GSK2141795.
- Fast for 2 hours after ingestion of the last capsule of GSK2141795. Water is allowed during this fasting period.
- In more severe cases, consider sucralfate and/or Gaviscon as supportive care to be taken at least 2hr after ingestion of the last capsule of GSK2141795, so as to avoid any potential drug-drug interactions.

## **5.2 General Concomitant Medication and Supportive Care Guidelines**

### **5.2.1 Permitted Medications**

Subjects will be instructed to inform the investigator prior to starting any new medications from the time of screening until the end of the clinical phase of the study. Any concomitant medications, including over-the-counter medications, herbal preparations and alternative therapies, taken during the study will be recorded in the CRF.

Subjects should receive full supportive care during the study, including transfusions of blood and blood products, erythropoietin and G-CSF support, and treatment with antibiotics, antiemetics, antidiarrheals, and analgesics, and other care as deemed appropriate, and in accordance with their institutional guidelines. Subjects should not receive those medications listed as prohibited in Section 5.2.2.

### **5.2.2 Prohibited Medications**

Subjects should not receive other anti-cancer therapy or other investigational drug while on study treatment, except for megestrol [Megace] if used as an appetite stimulant is allowed.

Patients should abstain from taking any herbal and dietary supplements within 5 half lives (or 14 days if the drug is a potential enzyme inducer) prior to the first dose of either study drug until completion of the follow-up visit, unless in the opinion of the Investigator and sponsor there is little concern for a potential drug-drug interaction with the study drug(s). These herbal medications include but are not limited to, St. John's wort, kava, ephedra (ma huang), ginkgo biloba, dehydroepiandrosterone (DHEA), yohimbe, saw palmetto, and ginseng. The investigator should contact a CTEP Medical Monitor before initiating treatment with any herbal preparation.

The following medications (including but not limited to) are prohibited during the study:

PROHIBITED – highly sensitive and/or low therapeutic index CYP3A/CYP2C8/BCRP/CYP3A4 substrates since concentrations of these drugs may be increased	
CYP3A Substrate	Therapeutic Area
Cisapride	Hypnotics and Sedatives
Pimozide	Antidepressant, Antipsychotics, Antianxiety agents
Astemizole	Antihistamine
BCRP Substrate	Therapeutic Area
Rosuvastatin, sulfasalazine	HMG-CoA Reductase Inhibitors, gastrointestinal agents
PROHIBITED – strong inducers/inhibitors of CYP3A4	
Strong CYP3A4 Inhibitor/Inducer	Therapeutic Area
clarithromycin, telithromycin, rifamycin class agents (e.g., rifampin, rifabutin, rifapentine), troleandomycin	Antibiotics
Itraconazole, ketoconazole	Antifungals
Nefazodone	Antidepressants
atazanvir, delaviridine, indinavir, lopinavir, nelfinavir, ritonavir, saquinavir, nevirapine	Antivirals
carbamazepine, phenobarbital, phenytoin	Anticonvulsants

### 5.2.3 Cautionary Medications:

The following medications (including but not limited to) that may alter the concentrations of trametinib or GSK2141795 or have their elimination altered by trametinib or GSK2141795 should be administered WITH CAUTION:

USE WITH CAUTION – Drugs Potentially Affecting trametinib or GSK2141795 concentrations	
Drug	Therapeutic Area
quinidine, diltiazem, verapamil	Antiarrhythmics:
fluvoxamine, fluoxetine, paroxetine, nefazodone	Antidepressants:
aprepitant, cimetidine	Antiemetics
fluconazole, terbinafine, voriconazole	Antifungals
ciprofloxacin, erythromycin, isoniazid	Anti-infectives
Mibefradil, diltiazem, verapamil	Calcium Channel Blockers
aprepitant, oxandrolone, tizanidine, gemfibrozil	Miscellaneous
USE WITH CAUTION – Drugs that may inhibit P-gp and BCRP	
Drug	Therapeutic Area
Valsopoda	Miscellaneous
Atorvastatin	HMG-CoA Reductase Inhibitors
Carvedilol	Congestive Heart Failure
Methadone	Analgesic
Meperidine	Narcotic
Omeprazole	Proton Pump Inhibitor
USE WITH CAUTION – Drugs that may have their concentrations altered by trametinib or	

GSK2141795	
Drug	Therapeutic Area
Repaglinide, rosiglitazone, pioglitazone	Antidiabetics
alfentanil, fentanyl	Analgesics
Quinidine	Antiarrhythmics
Cilostazole	Anticoagulants and Antiplatelets
Astemizole	Antihistamines
diergotamine, ergotamine, eletriptan	Antimigraine agents
Pimozide	Antipsychotics
Buspirone	Anxiolytics
Felodipine	Calcium Channel Blockers
sildenafil, tadalafil, vardenafil	Erectile Dysfunction agents
cerivastatin,ovastatin, simvastatin, atorvastatin	HMG-CoA Reductase Inhibitors
Alprazolam, diazepam, midazolam, triazolam	Hypnotics and Sedatives
cyclosporine, sirolimus, tacrolimus	Immunosuppressive agents
Cisapride	Prokinetic agents
cyclosporine, toseamide, chloroquine, zopiclone	Miscellaneous
Eperenone	Selective Aldosterone Blockers
chloroquine, zopiclone	Thiazolidinediones

Use of repaglinide, rosiglitazone, and/or pioglitazone is permitted only after consultation with the CTEP Medical Monitor.

Oral steroids should be used with caution and subjects monitored for steroid-induced hyperglycemia. Short courses (up to a maximum of 14 days) of oral corticosteroids intended to treat study treatment related rash or diarrhea are allowed. Budenoside is recommended for supportive care of diarrhea.

Subjects will be instructed to inform the investigator before taking any of these or any other medications. Investigators (or their appropriate designee) will be expected to review concomitant medications with the subject at each clinical visit. Because the lists of these agents are constantly changing, it is important to regularly consult a frequently-updated list such as <http://medicine.iupui.edu/clinpharm/ddis/table.aspx>; medical reference texts such as the Physicians' Desk Reference may also provide this information. As part of the enrollment/informed consent procedures, the patient will be counseled on the risk of interactions with other agents, and what to do if new medications need to be prescribed or if the patient is considering a new over-the-counter medicine or herbal product. Appendix C is a patient information sheet that can be used for this specific protocol and presented to the patient.

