#### Potential Drug-drug Interactions

In vitro data indicate that GSK2141795 is a CYP3A4 substrate. Drugs that potently inhibit CYP3A4 could lead to increased GSK2141795 exposure in subjects, and should either be prohibited or used with caution. Drugs that are strong inducers of CYP3A and may result in lower exposures of GSK2141795 should also be prohibited. GSK2141795 also appears to be a moderate in vitro inhibitor of CYP2C8 (50% inhibitory concentration [ $IC_{50}$ ] 3  $\mu$ M) and CYP3A4 ( $IC_{50}$  11  $\mu$ M). Drugs that are substrates of CYP3A4 or CYP2C8 with a narrow therapeutic index may be prohibited. Drugs that are sensitive substrates of CYP3A4 or CYP2C8 should be used with caution.

The following medications (including but not limited to) are prohibited during the study:

PROHIBITED – highly sensitive and/or low therapeutic index CYP3A/CYP2C8/BCRP/CYP3A4 substrates since concentrations of these drugs may be increased	
CYP3A Substrate	Therapeutic Area
cisapride	Hypnotics and Sedatives
pimozide	Antidepressant, Antipsychotics, Antianxiety agents
astemizole	Antihistamine
BCRP Substrate	Therapeutic Area
rosuvastatin, sulfasalazine	HMG-CoA Reductase Inhibitors, gastrointestinal agents
PROHIBITED – strong inducers/inhibitors of CYP3A4	
Strong CYP3A4 Inhibitor/Inducer	Therapeutic Area
clarithromycin, telithromycin, rifamycin class agents (e.g., rifampin, rifabutin, rifapentine), troleandomycin	Antibiotics
itraconazole, ketoconazole	Antifungals
nefazodone	Antidepressants
atazanvir, delaviridine, indinavir, lopinavir, nelfinavir, ritonavir, saquinavir, nevirapine	Antivirals
carbamazepine, phenobarbital, phenytoin	Anticonvulsants

For a list of medications that may alter the concentrations of trametinib or GSK2141795 or have their elimination altered by trametinib or GSK2141795 and thus should be administered WITH

CAUTION is provided in section 5.2.3.

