#### 8.1.2 GSK2141795 (NSC#)

**Chemical Name:** N-[(1S)-2-amino-1-[(3,4-difluorophenyl)methyl]ethyl]-5-chloro-4-(4-chloro-1-methyl-1H-pyrazol-5-yl)-2-furancarboxamide

**Other Names:** GSK2141795C

**Classification:** pan-AKT inhibitor

**CAS Registry Number:** 1047634-65-0

**Molecular Formula:** C18H16Cl2F2N4O2

**M.W.:** 429.25 g/mol

**Approximate Solubility:** Very slightly soluble in water at room temperature (0.18 mg/mL). Solubility decreases as pH increases; for example solubility in gastric fluid at 37° C is >11 mg/mL.

**Description:** white to off-white powder

**How Supplied:** GSK2141795 capsules are supplied by GlaxoSmithKline and distributed by the DCTD, NCI. The 25 mg capsule is a size 2 Swedish orange opaque body and Swedish orange opaque cap with no markings. The capsule contains active pharmaceutical ingredient, microcrystalline cellulose, and magnesium stearate. The capsules are packaged in white high density polyethylene (HDPE) bottles with white plastic, induction-seal, child-resistant caps. Each

bottle contains 35 capsules.

GSK does not have stability data to support repackaging GSK2141795 capsules. Capsules must be dispensed in the original container.

**Storage:** Store bottles at 2-8° C (36-46° F).

**Stability:** Shelf life studies of GSK2141795 are on-going.

**Route of Administration:** Oral administration. Capsules must be taken fasting 1 hour following a meal and 2 hours before the next meal. The following guidelines are recommended:

Eat a small snack followed by 60 minutes of fasting prior to taking GSK2141795. Water is allowed during this fasting period. If possible, take each GSK2141795 capsule approximately 5 minutes apart with divided amounts of fluid (4-8 oz with each capsule for a total of at least 12 oz). Remain upright for 30 minutes after taking the last capsule of GSK2141795.

Fast for 2 hours after ingestion of the last capsule of GSK2141795. Water is allowed during this fasting period.

**Potential Drug Interactions:** *In vitro* data suggest GSK2141795 is a substrate of CYP450 3A4. Potent inhibitors and inducers of 3A4 are prohibited. GSK2141795 appears to be a moderate inhibitor of CYP 2C8 and 3A4 by *in vitro* testing. Drugs that are substrates of these isoenzymes should be used with caution and ones with a narrow therapeutic index should be avoided.

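### Section 5.2.3 lists cisapride, pimozide, astemizole and nefazodone as usable with caution, although Section 5.2.2 prohibits all four

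*Combined protocol and SAP*

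**What the plan says.** Section 5.2.2 introduces its table with "The following medications (including but not limited to) are prohibited during the study". The table names cisapride, pimozide and astemizole as CYP3A substrates and nefazodone as a strong CYP3A4 inhibitor or inducer. Section 2.2.2 (Potential Drug-drug Interactions) carries the same table. Section 5.2.1 makes the list binding: "Subjects should not receive those medications listed as prohibited in Section 5.2.2".

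Section 5.2.3 lists drugs that "should be administered WITH CAUTION". In the block for drugs that may affect study-drug concentrations, the antidepressant row is "fluvoxamine, fluoxetine, paroxetine, nefazodone". In the block for drugs whose own concentrations may be altered, astemizole, pimozide and cisapride each have a row.

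Section 8.1.2 (Potential Drug Interactions) sets the rule by class for GSK2141795: "Potent inhibitors and inducers of 3A4 are prohibited", and of the CYP2C8 and CYP3A4 substrates, "ones with a narrow therapeutic index should be avoided".

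Exclusion 3.2.9 covers CYP3A4 and CYP2C8 drugs. Its only section reference is "Refer to 5.2.3".

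**The concern.** A drug cannot be both banned and allowed with caution. A site that checks a patient's medication against 5.2.3 alone would conclude that any of these four may be given. Exclusion 3.2.9 leads the site to that list and does not mention 5.2.2. Exclusion 3.2.8 bars current use of a prohibited medication, but the bullets beneath it name no CYP3A drug.

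The protocol states the risks itself. For nefazodone, Section 2.2.2 warns: "Drugs that potently inhibit CYP3A4 could lead to increased GSK2141795 exposure in subjects". The combination is given at 1.5 mg trametinib plus 50 mg GSK2141795, which Section 2.2.1.5 identifies as one of three maximum tolerated doses. For the other three drugs, the 5.2.2 table gives the risk as a rise in the co-medication's own concentration. A site that relied on 5.2.3 would also incur an avoidable protocol deviation.

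**Working it through.** The plan gives no figure to reproduce. The check compares the two lists drug by drug and then asks which one the rest of the protocol supports.

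**Count of drugs named in the 5.2.2 table**

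- CYP3A substrates: 3 (cisapride, pimozide, astemizole).
- BCRP substrates: 2 (rosuvastatin, sulfasalazine).
- Strong CYP3A4 inhibitors or inducers: 6 antibiotics (counting the three rifamycins given as examples) + 2 antifungals + 1 antidepressant + 8 antivirals + 3 anticonvulsants = 20.
- Total: 3 + 2 + 20 = 25.

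**Overlap with 5.2.3**

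| Group in 5.2.2 | Named | Also in 5.2.3 |
|---|---|---|
| CYP3A substrates | 3 | 3 |
| BCRP substrates | 2 | 0 |
| Strong CYP3A4 inhibitors/inducers | 20 | 1 (nefazodone) |
| Total | 25 | 4 |

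Removing the four entries from 5.2.3 brings the overlap to 4 − 4 = 0.

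**Which list is right**

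1. Two tables (2.2.2 and 5.2.2) ban the four by name. Only 5.2.3 allows them.
2. Section 5.2.1 forbids anything on the 5.2.2 list, without conditions.
3. Section 8.1.2 bans potent 3A4 inhibitors, which covers nefazodone as 5.2.2 classifies it. It also says narrow-index substrates should be avoided, and the 5.2.2 heading places the other three among highly sensitive or low-index substrates.
4. Section 2.2.2 gives its prohibited table and then points separately to 5.2.3 for cautionary drugs. The two lists are therefore meant to be different tiers.

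**Whether caution amounts to a ban in practice**

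It does not. Ciprofloxacin is on the 5.2.3 list, yet Section 5.2.4 recommends ciprofloxacin or moxifloxacin as infection prophylaxis in the first 4 cycles. Section 5.2.3 does require prior consultation with the Medical Monitor for repaglinide, rosiglitazone and pioglitazone, but it sets no such condition for the four drugs at issue.

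**The case against.** The strongest reply is that the protocol already settles the conflict. Section 5.2.1 bans by membership of the 5.2.2 list, and 5.2.3 never claims to override it. Section 5.2.2 comes immediately before 5.2.3 and is plainly titled. The pointer in 3.2.9 most naturally belongs to its sentence on cautious use, so it is not wrong as far as it goes. Section 5.2.3 also has patients tell the investigator before taking any medication and has medications reviewed at each clinic visit. On this view the point is editorial tidying.

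These safeguards lower the risk, but 5.2.1 helps only a reader who checks both lists, and 5.2.3 remains wrong as written.

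A second reply is that the class-level text is softer than the tables. Sections 2.2.2 and 3.2.9 leave potent CYP3A4 inhibitors open to either a ban or cautious use, and say only that narrow-index substrates may be banned. That is correct, and it sits awkwardly with 8.1.2. It does not move these four drugs into the caution tier, because 2.2.2 follows the same text with a table banning them by name.

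Third, the scope is narrow. Section 8.1.1 reports that trametinib itself is not a CYP substrate and has low interaction potential, and GSK2141795 is given only in the optional add-on phase. This stands. It also stands that both lists are open-ended, so 4 of 25 measures the extent of the contradiction and not a level of risk.

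**Conclusion.** The inconsistency is real, and the documents settle its direction: prohibition is the intended rule, and four entries in 5.2.3 are wrong. They cover 4 of 25 named prohibited drugs: 3 of 3 CYP3A substrates, 1 of 20 strong inhibitors or inducers, and 0 of 2 BCRP substrates. It should be corrected because 5.2.3 is a working safety instruction. It does not threaten the trial's validity: sample size, alpha, power and the primary endpoint are untouched.

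Two limits apply. The documents give no basis for estimating how many patients might take these drugs. Appendix C, the patient sheet on drug interactions, was not in the text available for review, so its treatment of these drugs was not checked.

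**What to change.** Keep all four drugs in 5.2.2. In 5.2.3, delete nefazodone from the antidepressant row and remove the astemizole, pimozide and cisapride rows. Change the pointer in 3.2.9 to: *Refer to 5.2.2 for prohibited and 5.2.3 for cautionary medications.* Add to 5.2.3: *If a drug appears in both sections, 5.2.2 governs.* Once the entries are gone, that sentence largely repeats 5.2.1, but it protects against a future overlap as the lists are updated. The table in 2.2.2 needs no change.

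The cost is amendment wording only: four table entries deleted, one cross-reference corrected and one sentence added. No design, data or analysis consequence follows.
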